Recent studies have highlighted the potential role of changes in the skin bacterial and fungal community—the skin microbiome—in exacerbating inflammation of atopic skin. The changes show differing dominating bacterial and fungal strains in healthy and diseased skin (Park 2017). Lesional skin has been shown to be dominated by *Staphylococcus* bacteria and contain a lower microbial diversity than adjacent non-lesional skin (Kong 2012, Seite 2014). It is hypothesized that *Staphylococcus aureus* plays a critical role in the pathogenesis of eczema: the density of *S. aureus* in eczema patients can be staggering at 10^7 colonies per square centimeter of atopic skin, representing a far greater burden than those observed in other forms of skin inflammation (Lin 2007, Cho 2001). *Staphylococcus* is also a major bacteria found on atopic scalps (Park 2017). Though the precise link between dysbiosis, eczema, and dry scalp in humans remains unclear, these results warrant further investigation into the role of antimicrobial therapy in reversing dysbiosis and its' potential exacerbation of disease severity.

The use of hydrating emollients is effective on atopic skin, in which dry cracks allow irritants to pass and exacerbate the condition (Hanifin et al 2004). Emollients have been found to change skin communities from a disease to healthy state (Seite 2014). Of especial relevance, a 2014 study showed that topically allied emollients containing *Lactobacillus sakei* were effective in a split body trial at reducing common symptoms of eczema (Park 2014). As topical therapy, honey has been shown to work synergistically with antibiotics to treat methicillin-resistant *S. aureus* (Liban 2013). Honey possesses the antibacterial potency needed to stop the growth of *S. aureus*. and histologic studies show early decreases in inflammation, better infection control, and faster healing times (Lusby 2002). In addition, curcumin, the

active ingredient in turmeric, has also shown to be beneficial in skin disease. Although research on curcumin is not extensive, it has demonstrated antioxidant and anti-inflammatory properties in preclinical trials. Its lack of toxicity, even at high doses, makes it an attractive, natural treatment option (Thangapazham et al 2007).

We aim to characterize the safety and efficacy of a topical preparation of *Lactobacillus sp.*, honey, and turmeric in an emollient base in restoring the scalps of those with dry scalp to more closely resemble the healthy scalps.

2. STUDY DESIGN AND SYNOPSIS:

This pilot study consists of participants diagnosed with dry scalp. Participants will receive the required topical vehicle with the treatment condition (containing dead bacteria) on their scalp. This study will consist of 15-40 participants' ages 1 years old to 17 years old and 20-40 participants 18 and older with a clinical diagnosis of dry scalp. Participants will be recruited either while visiting a dermatologist for a standard office visit, while visiting a pediatrician for a standard office visit, or by coming into Children's Healthcare Associates, Medical Dermatology, or our Northwestern research office to be assessed by a physician. Each study visit will take approximately 15-20 minutes.

No randomization will occur, as all participants will receive the active treatment. Each adult participant will apply the active treatment once daily for a study period of 14 days and discontinue using all other scalp management therapies. Each child participant (with the help of a caregiver, if needed) will apply the active treatment once every 2 to 3 days for a study period of 14 days and discontinue using all other scalp management therapies.

The primary goal of this study is to determine the safety and effectiveness of *Lactobacillus sp.*, honey, and turmeric in reducing dry scalp symptomology.

There are three goals in the comparison of these conditions:

- The first is to find the effectiveness of the active treatment in improving clinical disease severity. To accomplish this, an investigator will assess the severity of dry scalp before and after the treatment period using the 11-point flaking scale (Neumann 1996), respectively.
- The second goal is to determine whether the active treatment is safe. This will be accomplished by contacting the patient via over the phone and through daily emails designed to document adverse events and Overall Safety Score. The Overall Safety Score is a 4-point assessment ranging from "no signs of irritation" (0) to "patient discontinued due to irritation" (3). Participants will be asked about the Overall Safety score at the halfway point and the end point of the study.
- The third exploratory goal is to determine whether the microbiome can be changed. This will be

accomplished by obtaining swab samples from the participants' scalps, before and after the treatment period. The samples will be analyzed using 16s RNA sequencing and internal transcribed spacer (ITS) sequencing. Additionally, the change in colony count of bacterial and fungal colonies on the scalp before and after the treatment will be assessed using the Replicate Organism Detection and Counting (RODAC) method. We aim to characterize the effects of *Lactobacillus* sp., honey, and turmeric on dry scalps.

- Finally, this study will determine the quality of life of participants before and after the treatment period. Quality of life will be calculated using the ScalpDex tool, a validated 23-item instrument that explains the way that patients with scalp dermatitis are affected by symptoms, functioning, and emotions.

3. STUDY OBJECTIVES:

The first goal of this study is to determine the effectiveness of introducing *Lactobacillus* sp., honey, and turmeric, in reducing dry scalp symptomology.

Hypothesis 1a: Participants' scalps treated with vehicle plus *Lactobacillus* sp., honey, and turmeric preparation will exhibit decreased dry scalp severity on assessment by an investigator when compared to the scalps before treatment, as measured by an 11-point flaking scale.

The next objective is to determine the safety of introducing *Lactobacillus* sp., honey, and turmeric, in reducing dry scalp symptomology

Hypothesis 2a: The product containing *Lactobacillus* sp., honey, and turmeric will be safe for participant's scalps as measured by the Overall Safety Score and patient logs.

The final objective of this study is to compare the determine if an active *Lactobacillus*, honey, and turmeric topical preparation changes the microbiome after use for a dry scalp condition to more closely resemble healthy scalp

Hypothesis 3a: Participants' scalps treated with the active *Lactobacillus*, honey, and turmeric preparation will have a microbiome similar to those with healthy scalps.

4. STUDY POPULATION:

We aim to recruit participants with diagnosed dry scalp and with clinical signs on the scalp. Recruitment will consist of male and female participants. This will include 15-40 children between the ages of 1 year to 17 years old, and 20-40 adults over the age of 18.

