6.1. Primary Outcome Measures

The primary objective is to determine the safety and efficacy of YoBee in improving dry scalp conditions. Efficacy will be determined using the Investigator's Global Assessment (IGA) scale (Table 1), a 5-point assessment ranging from clear (0) to severe disease (4) and the Total Severity Scale (TSS) (Table 2), an assessment that averages erythema, scaling, and pruritus severity scores of scalp lesions. The TSS uses a 4-point scale ranging from none (0) to severe (3). Lastly, photographs of the scalp will be collected before and after treatment. Safety will be determined by contacting the patient via over the phone or through email to document adverse events and Overall Safety Score. The Overall Safety Score (Table 4) and the reporting of adverse events throughout the study will measure the safety of YoBee. The Overall Safety Score is a 4-point assessment ranging from “no signs of irritation” (0) to “patient discontinued due to irritation” (3). Participants will include the Overall Safety Score assessment in their daily journal.

An exploratory aim of this study is to find whether YoBee changes the microbiome after use for a dry scalp condition to more closely resemble healthy scalps. This will be accomplished by obtaining swab samples from the participants' scalps, before and after the treatment period. The samples will be analyzed using 16s RNA sequencing and internal transcribed spacer (ITS) sequencing. Additionally, the change in colony count of bacterial and fungal colonies on the scalp before and after the treatment will be assessed using the Replicate Organism Detection and Counting (RODAC) method. Finally, ScalpDex, a validated instrument, will assess the change in quality of life of participants. ScalpDex is a 23 question survey that will be administered electronically via RedCap to participants.

7. DATA DISCLOSURE AND SUBJECT CONFIDENTIALITY:

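### The efficacy goals credit Lactobacillus, honey and turmeric, but a single-arm before/after design can show only an uncontrolled change with the whole preparation

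*Combined protocol and SAP*

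**What the plan says.** **Allocation.** Section 2 says "No randomization will occur, as all participants will receive the active treatment". It also says "Participants will receive the required topical vehicle with the treatment condition (containing dead bacteria) on their scalp". The aim that closes the background describes the product as Lactobacillus with "honey, and turmeric in an emollient base in restoring the scalps of those with dry scalp". There is no vehicle-only, untreated or within-person control. Participants are also told to stop their other scalp therapies for the 14 days.

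**Goals.** In section 2, "The primary goal of this study is to determine the safety and effectiveness of" Lactobacillus, honey and turmeric for dry scalp symptoms. Section 3 opens in the same way: "The first goal of this study is to determine the effectiveness of introducing" those three ingredients. Section 2 also introduces its goals as a comparison between conditions, although only one condition exists. Section 6.1 is worded differently: "The primary objective is to determine the safety and efficacy of YoBee". That names the product.

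**Hypothesis and power.** Hypothesis 1a in section 3 compares severity after treatment with severity before it, in scalps treated with vehicle plus the ingredients. Section 10.1 likewise concerns a pre/post change.

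**Vehicle.** The background says "The use of hydrating emollients is effective on atopic skin", and "Emollients have been found to change skin communities from a disease to healthy state".

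**Limitations.** Section 11 lists participant bias and lack of diversity. It does not mention the absence of a control.

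**The concern.** The goals attribute an effect to three named ingredients. The only contrast available is each participant's severity before and after the complete preparation. That contrast mixes at least four things: the ingredients, the emollient vehicle (massaged in and rinsed off), the withdrawal of other products, and natural change, including regression to the mean in people enrolled because they have symptoms. The plan's own background does not treat emollients as inert, either for symptoms or for the microbiome that forms the exploratory aim.

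At stake is what may be concluded. If the report follows the goals as worded, a fall in severity could be presented as evidence that Lactobacillus, honey and turmeric work, even if they add nothing to the vehicle. Section 11 would give the reader no warning of this.

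**Working it through.** The mismatch rests on the text. The arithmetic only shows how easily a before/after test can be positive with no ingredient effect.

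**1. Goal against contrast**

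| Place | Credited with the effect | Contrast available |
|---|---|---|
| Section 2, primary goal | The three ingredients | None that isolates them |
| Section 3, first goal | The three ingredients | None that isolates them |
| Section 3, Hypothesis 1a | Vehicle plus ingredients | After versus before |
| Section 6.1 | The product, YoBee | After versus before, uncontrolled |

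Only Hypothesis 1a matches what the design delivers.

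**2. The plan's power figure.** Section 10.1 gives 80% power, alpha 0.05 and a one-point difference, but no SD, no sidedness and no single sample size. It can be neither reproduced nor refuted. Solving a two-sided paired t-test backwards, 80% power for one point needs an SD of change of 1.51 at n=20 or 2.20 at n=40, the ends of the adult range. Whatever the SD, this is power for a pre/post change and not for an ingredient effect.

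**3. Regression to the mean alone.** All inputs are assumed; the documents give none of them.
- Severity has SD 1 at each visit, so results are in SD units and do not depend on the scale used.
- Recruits average k SD above the mean of their source population at baseline, with k = 0.5 or 1.
- Test-retest correlation ρ is 0.6 or 0.8.
- No ingredient effect and no vehicle effect.

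Expected fall = (1 − ρ) × k. SD of change = √(2(1 − ρ)), which is √0.4 = 0.632 at ρ = 0.8 and √0.8 = 0.894 at ρ = 0.6. Noncentrality = (fall / SD of change) × √n. Power is for a two-sided paired t-test at 0.05 with n − 1 degrees of freedom.

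| k | ρ | Fall | Fall / SD of change | Significant, n=20 | Significant, n=40 |
|---|---|---|---|---|---|
| 0.5 | 0.8 | 0.1 | 0.158 | 10.3% | 16.4% |
| 0.5 | 0.6 | 0.2 | 0.224 | 15.8% | 28.1% |
| 1 | 0.8 | 0.2 | 0.316 | 26.9% | 49.6% |
| 1 | 0.6 | 0.4 | 0.447 | 47.6% | 78.8% |

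For example, with k = 1, ρ = 0.6 and n = 20, the noncentrality is 0.447 × √20 = 2.00, which gives 47.6%.

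**4. Any non-ingredient fall.** Suppose vehicle, withdrawal of other products and natural change together lower the score by 0.5 point, and the ingredients add nothing. The same test is significant 56.5% of the time at n=20 and 86.9% at n=40 if the SD of change is 1.0, or 29.4% and 53.8% if it is 1.5. The 0.5 point and both SDs are assumptions. A larger sample raises these percentages, because the test is then better at detecting a change that is not due to the ingredients.

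**The case against.** The strongest reply is that the text already supports a whole-product reading. The aim closing the background speaks of a preparation in an emollient base, the first bulleted goal in section 2 concerns the active treatment before and after, and Hypothesis 1a says vehicle plus ingredients. The single arm is disclosed openly in a self-described pilot. On this view the goal sentences are shorthand. Much of that stands: Hypothesis 1a is a fair before/after statement, and a single-arm pilot is a legitimate choice. But the two goal sentences leave the vehicle out, and nothing in section 11 corrects the impression.

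The illustration is also sensitive to its inputs. Section 4.1.1 sets no minimum severity score, and section 5 also recruits by mail and email from databases and prior interest, so nothing in the documents supports an offset as large as 1 SD. At 0.25 SD the percentages fall to 6% to 8% at n=20 and 8% to 11% at n=40. This stands, and is why the figures are given as a range and carry no weight in the finding itself.

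Four stronger readings are tempting, and the documents do not support them:
- *Section 6.1 also makes an ingredient claim.* It names only the product. The issue there is that efficacy is uncontrolled.
- *The plan counts any significant fall as proof of the first objective.* Section 10 names no test and no success rule.
- *The plan claims superiority over vehicle.* No section does.
- *The emollient is known to improve dry scalp.* The background's statement on symptoms concerns atopic skin, and this product is rinsed off after about five to seven minutes. A vehicle effect is plausible but not quantified. Nor is the direction of any effect of stopping other products known.

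**Conclusion.** The point holds as a mismatch between goal and design. The goals in sections 2 and 3 ask whether three ingredients are effective; the design can estimate only the uncontrolled 14-day change with the complete preparation. This follows from the text and needs no assumption about SD, correlation or vehicle effect.

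Its numerical size cannot be fixed from the documents. The range of 10% to 48% at n=20 and 16% to 79% at n=40 applies only for offsets of 0.5 to 1 SD and correlations of 0.6 to 0.8, and excludes any vehicle effect. The finding does not say that the pilot is invalid, that it needs a control arm, or that the ingredients do not work. It should be corrected because the correction is cheap and the unsupported attribution concerns the main efficacy claim.

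**What to change.** 1. Leave the safety objective unchanged wherever it appears.
2. In sections 2 and 3, reword the efficacy part of the goals to match Hypothesis 1a, for example: *estimate the 14-day change from baseline in severity with the complete preparation (vehicle plus Lactobacillus, honey and turmeric), without a control*. Make the same change to the efficacy part of section 6.1.
3. In section 2, remove the reference to a comparison of conditions.
4. In section 11, add that there is no control, and that no effect will be attributed to the ingredients or claimed over vehicle.
5. State that the observed SD of change, and not the mean change, will inform the planning of any vehicle-controlled trial. The mean change includes any vehicle effect and regression to the mean, so it is not an estimate of a between-arm difference.

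The cost is protocol wording, submitted to the IRB as section 13.3 requires. Sample size, visits and treatment do not change. The downside is a less favourable claim.

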Participants will be supplied with the scalp treatment and relevant instructions. Participants will be instructed to apply the preparation to their scalp. Adults will apply the scalp treatment on the site of active dry scalp once per day at home at a consistent time, every day for 14 days. Children will apply the hair care regimen at home at a consistent time two to three times a week over a 14-day period. -. Participants will be instructed to discontinue their regular scalp-care therapies. Adult participants will be contacted daily via email or telephone regarding scalp care regimen, usage of treatment, and any adverse events. Child participants will be contacted weekly via email or text regarding scalp care regimen, usage of treatment, and any adverse events. One week from the baseline visit (7 days), the participant will be contacted via phone, text or email to complete surveys regarding treatment experience and to confirm correct usage of treatment. Fourteen days following the baseline visit, adult participants will be seen, where repeat scalp cultures will be obtained via the swab and RODAC methods, and a repeat scalp flaking survey (IGA) (with photographs) will be assessed by a physician. Final experience surveys will be administered via REDCap. Fourteen days following the baseline visit, child participants will attend a secondary visit, where a physician will assess the participants' scalp and re-evaluate the IGA placement.

Study Schema

VISIT 1: (baseline)

- Recruitment and electronic informed consent of participants via REDCap.
- Obtain baseline scalp culture skin swabs from participant for microbiome diversity analysis.
- Obtain baseline scalp cultures from participant via RODAC method to obtain initial bacterial burden level. The RODAC (Replicate Organism Detection and Counting) method is used to measure the number of colony forming units (CFU) per skin surface area. The primary purpose of the RODAC method is to monitor presence and number of microorganisms as determined by the appearance of colonies on the surface of an agar medium.
- Local scalp flaking survey performed to the participant by investigator. Photographs will be taken.
- Administer baseline demographics survey via REDCap.
- Demonstrate/teach patients the treatment regimen. The treatment for adults will be applied daily for 14 days for 5 minutes. The treatment for children will be applied 2 to 3 times a week over the course of 14 days for 5 minutes.

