- Instruct adult participants to respond to the daily scalp care emails or phone calls. Instruct child participants to weekly scalp care emails, text messages, or phone calls.- Provide participants with all study materials, including instruction handout.
- Instructions for adults will be given stating: Wash your hands and make sure scalp/hair is dry, and then apply the treatment to your entire scalp. Massage the treatment in, wait around seven minutes, and then rinse it from your scalp. Please be sure to apply the treatment daily. Instructions for children will be given stating: Wash your hands and make sure scalp/hair is dry, and then apply the treatment to your entire scalp. Massage the treatment in, wait approximately five minutes, and then rinse it from your scalp. Please be sure to apply the treatment 2 to 3 times a week.

FOLLOW-UP:

- Study coordinator will contact participant or caregiver via phone or email daily to ensure safety of treatment regimen. [name] will follow-up with patients if adverse events are reported.
- Quality of life and overall safety score surveys will be sent to participants at the 7 day mark.

VISIT 2 at Lurie Children's, Northwestern University, or Medical Dermatology Associates of Chicago: (14 days after baseline)

- Obtain scalp culture skin swabs from patient for microbiome diversity analysis.
- Obtain scalp cultures from patient via RODAC method to obtain final bacterial burden level.

- Local scalp flaking survey performed to patient by investigator. Additional photographs will be taken.
- Ask participants to fill out the follow-up questionnaire via REDCap during the visit on a study iPad.

Events performed outside of patient visits:

-Skin swabs and RODAC plates will be transported from the collection site to the laboratory of [name] or to [name] lab at Rush University. The team will use an insulated carrier to transport the samples directly following each visit.

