For visit 1 and 2, the study visit will take place at either Lurie Children's, Northwestern University, Children's Healthcare Associates, or Medical Dermatology Associates of Chicago. A board certified Dermatologist, Allergist, or Physician/pediatrician will conduct a scalp assessment to determine whether the participant is eligible for the study. [name], the PI, will be the primary contact in the event of an adverse event, but will not be involved directly with any items in visit 1, the follow up, or visit 2. A research coordinator will consent the participant, explain the procedures of the study, swab the scalp, and administer the surveys. Either a research coordinator or physician will take pictures of the patient's scalp. The same responsibilities for the physician and research coordinator will take place at visit 2. For the adult follow ups, a research coordinator will either email or call the participant daily (based off their preference) regarding treatment use and adverse effects. Storage will occur at [name] Lab (Lurie Children's) and [name] lab at Rush University, and analysis will be done by [name] lab and [name] lab at Rush University.

Parents will be asked to perform the treatment on children ages 1-11, but children ages 12 years-17 years will be asked to perform the treatment themselves. Parents will complete surveys for all children regardless of age.

6. DATA COLLECTION AND REPORTING:

At baseline, culture swabs will be obtained from all patients' scalp via both the swab and RODAC method. Patients will fill out an intake survey including demographics via REDCap. The physician will complete a scalp flaking survey to evaluate initial disease severity.

At the 7-day mark, adult patients will be emailed or texted surveys to ensure the treatment regimen and daily instructions are being completed correctly as well as to assess the safety and efficacy of the treatment. At the 7-day mark, child patients will be emailed or texted surveys to ensure the treatment regimen and weekly instructions are being completed correctly as well as to assess the safety and

efficacy of the treatment. All questions will be answered and noted on a secure Northwestern server.

At the 14-day follow-up visit, cultures will again be obtained from the patients' scalp via the swab and RODAC methods. The investigator will complete the scalp flaking survey to evaluate endpoint disease severity. Patients will then fill out a follow-up questionnaire via REDCap.

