9. SAFETY ASSESSMENT

All of the ingredients contained in our topical formulation are either foods or commonly used in cosmetics and skin care products. As such, we have minimal reason to believe that participants will experience major adverse events from treatment. There may be a risk of mild irritation, given the nature of already inflamed skin, but this should be minimal as compared to current accepted topical treatments for dry scalp. This study utilizes dead *Lactobacillus* species to eliminate the risk of growth and thus, the risk of new disease or symptomatology. Furthermore, dead bacteria are easier to store and offer a longer shelf life, eliminating the risk of application of an unknown size or species of bacteria.

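### No Overall Safety Score is scheduled before the first application, so a later score cannot by itself show new or worsened irritation

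*Combined protocol and SAP*

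**What the plan says.** The combined protocol and SAP gives three timings for the Overall Safety Score:

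- Section 2 (Study Design and Synopsis): "Participants will be asked about the Overall Safety score at the halfway point and the end point of the study".
- Section 5, Study Schema, Follow-up list: "Quality of life and overall safety score surveys will be sent to participants at the 7 day mark".
- Section 6.1 (Primary Outcome Measures): "Participants will include the Overall Safety Score assessment in their daily journal".

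The scale is described in Sections 2 and 6.1: "The Overall Safety Score is a 4-point assessment ranging from" an anchor for absence of irritation (0) to one for discontinuation because of irritation (3). Section 6.1 refers to Table 4 for the score.

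For baseline, the Visit 1 list in Section 5 has swabs, RODAC cultures, the flaking survey, photographs and a questionnaire: "Administer baseline demographics survey via REDCap". Section 6 describes the questionnaire this way: "Patients will fill out an intake survey including demographics via REDCap". Neither section lists the Overall Safety Score at this visit.

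Safety is part of the primary objective in Section 6.1. Hypothesis 2a in Section 3 rests on this score together with patient logs. Section 2 states that everyone receives active treatment. Section 9 says of the expected harm: "There may be a risk of mild irritation, given the nature of already inflamed skin".

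**The concern.** The score is a level, not a change. Section 4 recruits people with clinical signs on the scalp, and Section 9 describes the skin as already inflamed. On the visible anchors, a participant could plausibly score above 0 before using the product. A post-treatment 1 or 2 could then be new irritation, worse irritation, unchanged disease or even improvement.

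With no control arm, each participant's own pre-treatment state is the only reference within the study. The plan uses that reference for flaking, the microbiome, colony counts and quality of life, but not for this score. The harm that the plan expects is mild, which is the range where existing signs and new signs overlap. At stake is whether the score can support the safety half of the primary objective. A harmless product could look irritating, or new irritation could pass as background disease.

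**Working it through.** The plan states no figure on this point, so the check is a comparison of the text, followed by illustrations with assumed rates.

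**1. Timing against the first application**

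| Place | Timing of the score | Pre-application value specified? |
|---|---|---|
| Section 2 | halfway and end | no |
| Section 5, Follow-up | day 7 | no |
| Section 6.1 | daily journal | no |
| Section 5, Visit 1; Section 6, baseline | score not listed | no |

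The three timings disagree with each other, but none of them provides a baseline value.

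**2. Expected scores of 1 or more if the product does nothing**

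Inputs: the minimum sample is 15 + 20 = 35 and the maximum is 40 + 40 = 80 (Section 4). The share p with irritation at entry is not given, so 10%, 30% and 50% are assumed, with all of it persisting. Formula: n × p.

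| p (assumed) | n = 35 | n = 80 |
|---|---|---|
| 10% | 3.5 | 8 |
| 30% | 10.5 | 24 |
| 50% | 17.5 | 40 |

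**3. What one observed rate could mean**

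Suppose 30% score 1 or more on treatment (assumed). Let p0 be the share irritated at entry and s the fraction of those in whom it persists. New-onset irritation among those clear at entry is (0.30 − p0 × s) / (1 − p0).

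| p0 (assumed) | s = 1 | s = 0.5 |
|---|---|---|
| 0% | 0.30 / 1 = 30% | 0.30 / 1 = 30% |
| 10% | 0.20 / 0.90 = 22% | 0.25 / 0.90 = 28% |
| 20% | 0.10 / 0.80 = 12.5% | 0.20 / 0.80 = 25% |
| 30% | 0 / 0.70 = 0% | 0.15 / 0.70 = 21% |

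The same recorded 30% is compatible with new-onset rates from 0% to 30%. The post-treatment score alone cannot tell these cases apart.

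**4. Whether other measures fill the gap**

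- *Photographs*: taken at both visits, but no reading or scoring is described, and they cannot show itch.
- *ScalpDex*: Section 2 intends it before and after treatment, but the Visit 1 list omits it. It measures quality of life.
- *Physician assessment*: done at both visits, but the flaking scale does not grade irritation.
- *Adverse-event contacts*: these begin once treatment has started, with no recorded irritation baseline for comparison.
- *TSS*: Section 6.1 calls it "an assessment that averages erythema, scaling, and pruritus severity scores of scalp lesions". It is in no visit list, and averaging can hide opposite movements. Take chosen values of scaling 3 to 1, erythema 0 to 1 and pruritus 1 to 2. The mean before is (3 + 0 + 1)/3 = 1.33, and after is (1 + 1 + 2)/3 = 1.33, although two irritation signs worsened.

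**The case against.** The strongest reply is that the text read for this review does not contain Table 4, so levels 1 and 2 are unknown. The top anchor concerns a reaction to treatment. If levels 1 and 2 are also worded that way, an untreated scalp would not score above 0 and a baseline value would mean little. Section 9 can likewise be read as treating irritation as a treatment risk distinct from existing inflammation. This stands as a limit on confidence. It does not supply a baseline, and the lowest anchor as printed refers to signs of irritation without attributing them to the product.

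It is also fair that the baseline questionnaire is described as including demographics, so its content may be wider, and that Hypothesis 2a relies on patient logs as well as the score. Adverse-event reports can capture onset and worsening. Photographs and physician examination at both visits can show new redness. These allow partial separation.

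Two stronger readings are tempting. A reader might infer that existing irritation will be counted as product irritation. The documents do not support this, because they give no rule for counting or attributing scores of 1 or 2. A reader might also infer that worsening cannot be separated from existing disease at all. That is true of the score taken alone, not of the study as a whole, given the other records.

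**Conclusion.** The concern holds in a limited form. No stated schedule gives an Overall Safety Score before the first application, so no change from baseline can be computed on a named primary safety measure. In a single-arm study of scalps with existing signs, a later score below the discontinuation level cannot by itself be read as new or worsened irritation. The discontinuation level has no baseline equivalent and is not affected in the same way.

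The absence of a scheduled baseline score rests on the text alone. Its practical importance rests on the assumption that levels 1 and 2 describe irritation present, whatever its cause. The size cannot be estimated from the documents, and the counts in the working are illustrations that depend on assumed rates and persistence. The change should be made before enrolment, because a participant's baseline cannot be recovered after the first application.

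**What to change.** - Add the Overall Safety Score levels below discontinuation to the Visit 1 REDCap baseline survey, completed before the first application.
- Reconcile the three timings in Sections 2, 5 and 6.1 into one schedule.
- Define the safety result on this score as new or worsened irritation, and report it as a shift table from baseline. Report discontinuation for irritation separately.
- Where the TSS is scored, also report erythema and pruritus separately, before and after treatment.

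The cost is one item in an existing survey and one extra table, with negligible respondent time. The remedy has a limit that the report should state. With no control arm, and with participants also stopping their other scalp therapies, a baseline score would show worsening but would not establish that the product caused it.
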